4.2 Inclusion Criteria

Patients

1. Age 65-89
2. English speaking
3. Women and men
4. Of varying race/ethnicity
5. Accompanied to primary care visits at the Center on Aging by a family caregiver
 - 5.1. Family caregiver also consents to participating in this study.
6. Sufficient cognitive capacity to consent themselves or through a legal representative

Caregivers

1. Age 21+
2. English speaking

3. Women and men
4. Of varying race/ethnicity
5. Accompany an older adult to his or her primary care visits at the Center on Aging
 - 5.1. Older adult also consents to participating in this study.
6. Cognitively intact (on basis of a 6-item cognitive screen)

Clinicians

1. Age 21+
2. Women and men
3. Of varying race/ethnicity
4. Treat patients at the Center on Aging

4.3 Exclusion Criteria

1. Patients, caregivers, and clinicians that do not meet the inclusion criteria.
2. Patients and caregivers who are deaf or have hearing impairments that limit their ability to answer telephone queries.
3. Caregivers who are visually impaired and cannot see well enough to read large print and complete paper-based surveys.
4. Patients and/or caregivers whose dyad counterpart does *not* consent to take part in the study (i.e., Patients gives consent and their caregiver does not).

4.4 Strategies for Recruitment and Retention

Co-investigators will meet with clinicians who see patients at the Center on Aging to make them aware of the study protocol, including the request for their participation in the study and the plan to send recruitment letters (postal mail or email) to their patients and their family caregivers. An IRB-approved, informative study flyer will be sent with the recruitment letters (via postal mail or email). These meetings will be by phone, Zoom, or in-person if/when feasible. Co-investigators will review the consent form with each clinician, [allowing for questions and reminding him or her that participation is voluntary](#). The co-investigator will subsequently ask each clinician who agrees to a) complete the pre-intervention survey (which will be administered orally by the trained co-investigator) and b) review his or her patient list and identify individuals who typically attend appointments with a caregiver (family or friend). When meeting with these clinicians, co-investigators will verify that the caregiver lives with the patient and/or obtain the caregiver contact information from the providers. A study team member will then query EPIC to determine the dates of upcoming appointments for those patients. Pre-notification recruitment letters will then be sent by mail, email (when available), or Weill/EPIC Connect to the patients and caregivers of the identified patients one month prior to his or her next scheduled appointment. Recruitment letters may also be sent to potential participants via EPIC Pool of WCM/NYP Consent to be Contacted for Research (CCR) patients and chart review to determine potential eligibility. When possible, letters will be sent to the emergency contact (i.e., caregiver) if their telephone matches that of the patient, or by email. The recruitment letter will describe the study and advise potential participants that they may decline participation by emailing or placing a telephone call to the study team. Approximately two weeks after the initial letter (postal mail or email) is sent, patients and caregivers who have not opted-out will be telephoned or emailed by the trained co-investigator to confirm their interest. Participants complete the consent form and pre-visit survey over the

phone, for both their convenience and safety during the COVID-19 pandemic. COA waiting rooms are presently closed and patients/caregivers are met at the door and brought immediately to an exam room. Once these restrictions are lifted, patient/caregiver participants will be given the option to complete their informed consent process and study pre-visit survey in the waiting room prior to the patient's next visit. Participants who elect to do so in person will be asked to arrive 30 minutes prior to their scheduled visit to ensure sufficient time to review the consent form and complete the survey.

Trained co-investigators will use the caregivers' preferred method of contact to inform them about the study (phone or email) after sending the pre-notification letter. If it is safe to do so and if time allows, co-investigators may choose to have participants consent in-person at The Center on Aging, and in that case, they will also be given the first survey at this time prior to their health visit.

Caregivers in both the intervention and control group will be voluntarily compensated \$25 via AmEx gift cards for their participation in the initial post-visit survey. They will receive an additional \$10 via ClinCards for their participation in each of the follow up surveys (at 2 months and 6 months). In total, caregivers may be compensated up to \$45.

5. Registration Procedures

5.1 Subject Registration (WCM only)

Subjects will be registered within the WRG-CT as per the standard operating procedure for Subject Registration.

5.2 Subject Registration (Sub-sites)

N/A

6. Study Procedures

6.1 Schedule of Assessments

Table 1. Schedule of events

	Pre-Study	Pre-visit (Baseline)	Visit 1	Post-visit 1 (within 1 week of Visit)	Post-visit 2 (2-month follow-up)	Post-visit 3 (6-month follow-up)	Post- intervention
Cognitive Screen	X						
Informed Consent	X						
Demographics		X					
Caregiver Surveys		X		X	X	X	
Clinician Surveys		X					X

Audio-Recording of Medical Visit			X				
Medical Chart Abstraction	X						
Medical Events Log Six Months Post						X	

7. Data Reporting / Regulatory Considerations

7.1 Data Collection

The data collection plan for this study is to utilize REDCap to capture all data for all enrolled subjects.

7.1.1 REDCap

REDCap (Research Electronic Data Capture) is a free data management software system that is fully supported by the Weill-Cornell Medical Center CTSC. It is a tool for the creation of customized, secure data management systems that include Web-based data-entry forms, reporting tools, and a full array of security features including user and group-based privileges, authentication using institution LDAP system, with a full audit trail of data manipulation and export procedures. REDCap is maintained on CTSC-owned servers that are backed up nightly and support encrypted (SSL-based) connections. Nationally, the software is developed, enhanced and supported through a multi-institutional consortium led by the Vanderbilt University CTSA.

7.2 Regulatory Considerations

7.2.1 Institutional Review Board/Ethics Committee Approval

As required by local regulations, the Investigator will ensure all legal aspects are covered, and approval of the appropriate regulatory bodies obtained, before study initiation.

Before initiation of the study at each study center, the protocol, the ICF, other written material given to the patients, and any other relevant study documentation will be submitted to the appropriate Ethics Committee. Written approval of the study and all relevant study information must be obtained before the study center can be initiated or the IP is released to the Investigator. Any necessary extensions or renewals of IEC/IRB approval must be obtained for changes to the study, such as amendments to the protocol, the ICF, or other study documentation. The written approval of the IEC/IRB together with the approved ICF must be filed in the study files.

The Investigator will report promptly to the IEC/IRB any new information that may adversely affect the safety of the subjects or the conduct of the study. The

Investigator will submit written summaries of the study status to the IEC/IRB as required. On completion of the study, the IEC/IRB will be notified that the study has ended.

All agreed protocol amendments will be clearly recorded on a protocol amendment form and will be signed and dated by the original protocol approving signatories. All protocol amendments will be submitted to the relevant institutional IEC/IRB for approval before implementation, as required by local regulations. The only exception will be when the amendment is necessary to eliminate an immediate hazard to the trial participants. In this case, the necessary action will be taken first, with the relevant protocol amendment following shortly thereafter.

Once protocol amendments or consent form modifications are implemented at the lead site, Weill Cornell Medicine, updated documents will be provided to participating sites. Weill Cornell Medicine must approve all consent form changes prior to local IRB submission.

Relevant study documentation will be submitted to the regulatory authorities of the participating countries, according to local/national requirements, for review and approval before the beginning of the study. On completion of the study, the regulatory authorities will be notified that the study has ended.

7.2.2 Ethical Conduct of the Study

The Investigators and all parties involved should conduct this study in adherence to the ethical principles based on the Declaration of Helsinki, GCP, ICH guidelines and the applicable national and local laws and regulatory requirements.

This study will be conducted under a protocol reviewed and approved by the applicable ethics committees and investigations will be undertaken by scientifically and medically qualified persons, where the benefits of the study are in proportion to the risks.

This study will have been reviewed by the WCM IRB, Protocol Review and Monitoring Committee, and the Data Safety and Monitoring Committee (WCM DSMC), prior to conducting any human subjects research activities. The WCM Data Safety and Monitoring Committee has determined that their oversight & monitoring is not required for this low-risk study. Only surveys and chart abstraction are involved and it does not involve the evaluation of intervention on health outcomes of human subjects.

7.2.3 Informed Consent

The co-investigator or qualified designee must obtain documented consent according to ICH-GCP and local regulations, as applicable, from each potential subject or each subject's legally authorized representative prior to participating in the research study. Subjects who agree to participate will receive an oral consent document prior to speaking to a co-investigator.

Informed Consent will occur prior to administration of the pre-visit survey (for caregivers) and pre-intervention survey (for clinicians), by oral consent for participants until in-person

consent measures are safely feasible. For oral consent, a member of the study team will review the ICF in-full (see Oral Consent Script attachment) by phone, allowing for questions and reminding the potential subject that participation is voluntary. Oral confirmation of consent to participate will be documented by the study team member.

Older adults – who are the focus of this study – are at higher risk of severe illness from COVID-19. To minimize exposure of this vulnerable group, we are requesting a waiver of documentation of written consent. We have two points of justification. First, administering oral, rather than written consent would reduce the time participants spend in the waiting room prior to the study and unnecessary contact (i.e. with study co-investigators). Second, given that the Center on Aging is conducting a combination of video and in-person visits, oral consent is needed in order to accommodate those participants who cannot leave their homes at this time.

The initial ICF, any subsequent revised written ICF and any written information provided to the subject must be approved by IRB prior to use. The ICF will adhere to IRB/IEC requirements, applicable laws, and regulations.

7.2.4 Compliance with Trial Registration and Results Posting Requirements

Under the terms of the Food and Drug Administration Modernization Act (FDAMA) and the Food and Drug Administration Amendments Act (FDAAA), the Sponsor-Investigator of the trial is solely responsible for determining whether the trial and its results are subject to the requirements for submission to <http://www.clinicaltrials.gov>. Information posted will allow subjects to identify potentially appropriate trials for their disease conditions and pursue participation by calling a central contact number for further information on appropriate trial locations and trial site contact information.

7.2.5 Record Retention

Essential documents are those documents that individually and collectively permit evaluation of the study and quality of the data produced. After completion of the study, all documents and data relating to the study will be kept in an orderly manner by the Investigator in a secure study file. Essential documents should be retained for 2 years after the final marketing approval in an ICH region or for at least 2 years since the discontinuation of clinical development of the IP. In addition, all subject medical records and other source documentation will be kept for the maximum time permitted by the hospital, institution, or medical practice.

8. Statistical Considerations

Feasibility and acceptability will be examined by conducting frequency and descriptive statistics (i.e. mean, median, standard deviation, range) for enrollment rates and Likert-scale items assessing satisfaction with CHEC and perceived helpfulness.

Effectiveness will be measured by the number of completed checklists that result in a conversation with providers about caregiver needs and the receipt of relevant support. The effect of CHEC on the primary outcome variable, discussion of caregivers' needs, will be examined in a general linear mixed model with intervention group and time (pre-posttest) as fixed classification

factors, and individuals as levels of a random classification factor. The model will account for pre-intervention measures and will include a group x time interaction. Additional covariates (e.g., caregiver and care recipient age) and fixed classification factors (e.g., caregiver gender, race) will also be examined. Prior to model fitting, the distribution of all study variables will be assessed.

9. Adverse Event Reporting Requirements

Adverse event (AE) monitoring and reporting is a routine part of clinical research. Safety is monitored by evaluation of adverse events reported by subjects or observed by investigators or research staff, as well as by other investigations such as clinical laboratory tests, x-rays, electrocardiographs, etc.

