1.1 Study Objectives

1.1.1 Objectives

Objective 1: To demonstrate the feasibility and acceptability of CHEC in primary care practice.

Objective 2: To test the preliminary impact of CHEC on primary care visit communication (discussion of family caregivers' needs).

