1.1.2 Hypotheses / Research Questions

Hypothesis 1: Greater than 70% of caregivers will perceive the checklist to be an acceptable length and easy to use.

Hypothesis 2: Greater than 70% of caregivers will report that the checklist is helpful in identifying their unmet needs and starting a discussion with providers.

Hypothesis 3: Greater than 70% of caregivers and providers will report that they desire to continue using the checklist in the future.

Hypothesis 4: The checklist will not significantly impact primary care workflow or visit duration.

Hypothesis 5: Discussion of caregivers' needs and concerns will occur more often in the intervention group than in the usual care group.

Hypothesis 6: Caregiver perceptions of visit communication will be more positive in the intervention group than in the usual care group.

2. Background and Significance

In the United States, nearly 8 million older adults rely on family and other unpaid caregivers (neighbors; friends) for assistance with their health care. These caregivers collectively provide 75-80% of the total care hours to community-dwelling older adults and fill multiple roles in the health care system: attending doctor's visits, coordinating care, and assisting with treatment regimens. The availability and adequacy of assistance provided by family and unpaid caregivers have direct implications for health care costs and quality of care of older adults. Yet, caregivers are not systematically identified in care delivery systems, and their abilities and needs are not routinely assessed. Caregivers receive inadequate preparation for the tasks they must assume. They report high levels of stress and are at risk for physical illness, depression and anxiety, and sleep disturbance. If these impairments and unmet needs are not assessed and addressed, they can impede the caregiver's ability to provide effective assistance to the older adult, ultimately leading to costly hospitalizations and nursing home placements. These caregiver factors (health impairments; unmet needs) are particularly influential in the context of dementia where patients require substantial caregiving assistance.

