3.1 Overall Design

Clinicians who see patients at the Center on Aging (COA) will be made aware of the study via individual meetings with co-investigators. These meetings will be by phone, Zoom, or in-person if/when feasible. Patients and caregivers will be identified through referrals from physicians practicing at the Center on Aging. They will be sent a recruitment letter in the mail one month prior to a co-investigator calling them to go over the screening and consent forms. Any study data collected for potential participants that do not meet eligibility will be immediately deleted. Informed Consent and HIPAA authorization for caregivers and patients, and informed consent for clinicians will occur orally over the phone or in-person at the COA just prior to in-person health visits when feasible as outlined in the Informed Consent section.

Patient-caregiver dyads will be randomized into either the CHEC (n=60; 30 caregivers and 30 patients) or control (usual care) condition (n=60; 30 caregivers and 30 patients). Randomization will occur through block randomization with alternative block sizes of 4 and 6 for each participating clinician.

Intervention Condition. Participants in the intervention condition will complete the Caregiver Checklist portion of CHEC at the beginning of their health visit. The participating clinician will then respond to the checklist following the guidelines on the accompanying Tip Sheet.

Control Condition. Caregivers in the control condition will receive their usual care from the participating clinician during the health visit.

Baseline (pre-visit). Caregivers in both conditions will be asked to complete identical pre-visit surveys. The survey will be scheduled to be completed over the phone, digitally on REDCap, or in-person depending on the participant's preference and COVID-19-related guidelines. We will ask about the participant's background, caregiving role, communication with providers, and feelings of caregiver preparedness. It will take approximately 20 minutes to complete. Medical chart abstraction will be used to collect patient's background characteristics, medications, diseases, and health events (e.g., hospitalization). Clinicians will complete a pre-intervention survey over the phone or in-person depending on the participant's preference and COVID-19-related guidelines. We will ask for the clinicians' personal characteristics and preparedness to assess and address caregivers' needs and concerns.

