Visit. All participants will have their medical visit audio recorded.

Post-visit. All caregiver participants will complete a post-visit survey within 1 week of the visit. They will also complete follow-up surveys 2 months and 6 months after the visit.

Post-intervention. At the completion of the entire intervention period, clinicians will complete a post-intervention survey and interview. The clinician surveys and interview will take no more than 30 minutes total and will be conducted within 1 month of the conclusion of the intervention period.

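### Section 8 fits a pre/post group x time mixed model to discussion of caregivers' needs but identifies no pre-visit measure of it; scored at the one recorded visit, the interaction is not estimable

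*Combined protocol and SAP*

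**What the plan says.** Section 8 (Statistical Considerations) calls discussion of caregivers' needs the primary outcome variable and states that its effect "will be examined in a general linear mixed model with intervention group and time (pre-posttest) as fixed classification" factors, with individuals as a random factor. It adds: "The model will account for pre-intervention measures and will include a group x time interaction". The pre-intervention measures are not named.

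Objective 2 (Section 1.1.1) treats this outcome as communication in the primary care visit. Hypothesis 5 (Section 1.1.2) is a between-arm statement: "Discussion of caregivers' needs and concerns will occur more often in the intervention group than in the usual care group".

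On timing, Section 3.1 says: "Participants in the intervention condition will complete the Caregiver Checklist portion of CHEC at the beginning of their health visit". On recording, it says: "All participants will have their medical visit audio recorded". Table 1 in Section 6.1 has a single visit column with a single recording mark. The pre-visit caregiver survey is described in Section 3.1: "We will ask about the participant's background, caregiving role, communication with providers, and feelings of caregiver preparedness". Section 3.2 B lists a pre-test questionnaire and a 1-week post-test survey for caregivers in both arms. It says the instruments are attached to the IRB application, so their items are not in the document.

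**The concern.** A group x time interaction compares change between arms, so it needs the same outcome measured before and after the intervention. The plan places this outcome at a visit that occurs once and begins, in the intervention arm, with the checklist. That visit cannot also supply the pre value, and no other source of one is identified.

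This is the only inferential model in the plan. If Section 8 stands, someone must decide after data collection what counts as the pre measure, which terms to drop and how discussion is scored. Those choices could move the one between-arm result on visit communication that the pilot is meant to give. The weight is moderate. Section 8 calls the outcome primary, but the synopsis puts it under a secondary, preliminary objective, and its primary endpoints list a count of checklists leading to a conversation, not a between-arm comparison of discussion.

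**Working it through.** **Inputs.** 60 dyads, 30 per arm (Section 3.1); model terms from Section 8; one recorded visit per dyad (Section 6.1, Table 1). The plan gives no event rate, correlation, power or precision target for this outcome, so it has no figure to reproduce. All rates and correlations below are assumptions.

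**Step 1. Possible sources of a pre value.**
- Visit recording: one per dyad, made at the visit that starts with the checklist in the intervention arm.
- Chart abstraction (Sections 3.1 and 3.2 A): background, medications, diagnoses and health events; nothing on discussion.
- Count of checklists leading to a conversation: no value before the visit and none in the control arm.
- Pre-visit survey: covers communication with providers in general terms; items not shown.

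**Step 2. One record per dyad (60 rows).** With group g and time t = 1 for everyone, each row of [1, g, t, g x t] is (1, g, 1, g). The time column equals the intercept and the interaction column equals group, so the rank is 2 of 4. Time and group x time are not estimable. The sum of the group and interaction coefficients, which is the arm difference at the visit, is estimable.

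The covariance is (individual variance + residual variance) x identity, so only the sum is identified. As a check on one simulated 60-record data set with total variance 0.24, the REML log-likelihood was 12.3602 at all five individual/residual splits tried (0/0.24, 0.06/0.18, 0.12/0.12, 0.18/0.06, 0.24/0).

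**Step 3. One pre and one post record (120 rows).** The rank is 4 of 4 and the interaction is estimable. Take equal variance s² at both occasions and correlation rho:
- Visit-only arm difference: SE = s x sqrt(2/30).
- Group x time: the change has variance 2s²(1 − rho), so the SE is sqrt(2(1 − rho)) times the visit-only SE.
- Pre item as baseline covariate: the residual variance is s²(1 − rho²), so the SE is sqrt(1 − rho²) times the visit-only SE.

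| Assumed rho | Group x time | Baseline covariate |
|---|---|---|
| 0 | 1.41 | 1.00 |
| 0.3 | 1.18 | 0.95 |
| 0.5 | 1.00 | 0.87 |
| 0.7 | 0.77 | 0.71 |

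The ratio of the two is sqrt(2(1 − rho)) / sqrt((1 − rho)(1 + rho)) = sqrt(2/(1 + rho)), which exceeds 1 for every rho below 1. Below rho = 0.5 the interaction is also less precise than ignoring the pre item.

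A simulation with yes/no measures (pre item 30% in both arms, visit outcome 30% vs 50%, 20,000 runs) gave 1.96 x SD of about 0.24 visit-only. At correlations 0, 0.3 and 0.5, group x time gave 0.335, 0.282 and 0.240, and the covariate analysis gave 0.244, 0.235 and 0.213. The ordering agrees with the formulas.

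**Step 4. Precision of the visit-level comparison.** The unstratified half-width is 1.96 x sqrt((p1(1 − p1) + p2(1 − p2))/30). For 10% vs 30%: 1.96 x sqrt((0.09 + 0.21)/30) = 0.196. For 30% vs 50%: 1.96 x sqrt((0.21 + 0.25)/30) = 0.243.

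A Mantel-Haenszel risk difference over 10 clinicians with 6 dyads each (20,000 runs) gave mean half-widths of 0.192 (10% vs 30%), 0.222 (20% vs 40%), 0.238 (30% vs 50%) and 0.238 (50% vs 70%), with coverage of 93.6% to 93.9%. Each scenario assumes a 20-point difference, so in three of the four the half-width exceeds the difference.

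**The case against.** The strongest reply is that Section 8's reference to pre- and post-test matches the names of the caregiver instruments in Section 3.2 B: a pre-test questionnaire and a 1-week post-test survey, given in both arms. Individuals as a random factor also fits caregivers surveyed more than once. The pre-visit survey asks about communication with providers, and a listed scale on perceptions of visit communication could contain a relevant item. No section says that discussion is scored from the recording. If a caregiver-reported version exists, there are two records per caregiver and the interaction can be estimated.

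This stands as far as it goes: non-estimability is conditional on scoring at the visit. A reader might infer that the model cannot be fitted at all, or that no pre-visit item exists. The documents support neither, because the items are not shown.

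It does not rescue Section 8. No such item is named, and the study-developed questions are described as covering the screening tool and resources. A report of earlier communication is also a different measure from whether discussion took place at this visit, which is what Hypothesis 5 compares. Even with a suitable item, Step 3 shows that the interaction is the less precise choice.

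A second reply is that this is a pilot whose main aim is feasibility and acceptability. That limits the weight of the point but does not supply the missing measure.

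**Conclusion.** The point holds in conditional form and should be fixed. Section 8 specifies a pre/post model for an outcome with no identified pre-visit measure. Scored at the visit, as Objective 2 and Hypothesis 5 imply, two of the four fixed effects and the individual variance are not identifiable; this needs no assumed rates. Scored from surveys, the interaction is estimable but less precise than baseline adjustment at every correlation below 1, given equal pre and post variances. Section 8 needs amending on either reading.

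A reader might also conclude that Hypothesis 5 cannot be tested. That does not follow: the arm difference at the visit is estimable in both cases. At 30 vs 30 with complete data and the assumed rates, its 95% CI half-width is about 0.19 to 0.24, roughly the size of the assumed 20-point difference. The result would be a preliminary estimate only, and the plan states no precision target against which to judge it.

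**What to change.** Before analysis, amend Section 8 as follows.

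- Define whether caregiver needs were discussed at Visit 1, identically in both arms, with a stated source and a written coding rule. If the source is the 1-week survey, which has separate intervention and control versions, confirm that both carry the same item.
- For this outcome, drop time, group x time and the individual random effect.
- Report the between-arm difference with a 95% CI, accounting for clinician as the randomisation stratum, since Section 3.1 says: "Randomization will occur through block randomization with alternative block sizes of 4 and 6 for each participating clinician". Use a method suited to the outcome's scale, for example a Mantel-Haenszel risk difference if it is yes/no.
- If a pre-visit item exists, name it and use it as a baseline covariate.
- If recordings are the source, report the number missing by arm. Section 3.2 A makes voice and video recordings voluntary, while Section 3.1 expects one for every participant.
- Report the count of checklists leading to a conversation descriptively, in the CHEC arm only, because it has no control-arm counterpart.

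The cost is rewriting part of Section 8, writing the coding rule, and some coding time on recordings and transcripts already planned. No new participants, visits, surveys or recordings are needed.
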